8.3.2 Other safety related information

Injection site reactions (ISR) including individual signs or symptoms at the injection site following investigational product administration should be recorded on specifically designed eCRF pages.

Other safety related information that should be reported as adverse events in accordance with the process described in section 8.4 are:

- Potential anaphylactic reactions assessed by Sampson criteria ([APPENDIX A](#)). If Sampson criteria are positive, confirm by elevation of tryptase in blood plasma measured within 30 minutes of symptoms
- Hyperglycemia-related AEs:

Report 'New onset of diabetes' in subjects with no medical history of diabetes when:

- HbA1C becomes $\geq 6.5\%$ and/or
- If a new concomitant medication for control of plasma glucose is added, further information to assess for a diagnosis of new onset diabetes will be collected

Report 'Worsening of the glycemic control' or 'diabetic complications' in subjects with a medical history of disease (HbA1C $\geq 6.5\%$ at baseline) when:

- HbA1C increases from baseline $> 0.5\%$ and/or
- New concomitant medication or increase in dose of current antidiabetic therapy is initiated to improve the control of plasma glucose level

8.4 Procedure for Adverse Event Reporting

8.4.1 Serious Adverse Events (SAEs)

All SAEs that occur from consent (Day1) through EOS must be reported to Novartis safety within 24 hours of awareness of the event using the provided study specific SAE Report Form. Each SAE must also be recorded on the source documents and on the appropriate page of the eCRF.

The investigator should provide any follow-up information for the event to the Sponsor on an updated SAE Report Form as soon as it becomes available. The Sponsor will contact the investigator, if necessary, to clarify any of the event information or request additional information.

If the investigator is notified of a SAE that occurs post-study period, that he or she wishes to report to the Sponsor (eg, an event suspected to be causally related to investigational product), the event should be reported through the process described above.

Where appropriate, if required by local regulations or procedures, the investigator should report these events to the Institutional Review Board (IRB)/Ethics Committee (EC) and/or national regulatory authority in addition to the Sponsor.

Detailed instructions regarding the submission process and requirements are to be found in the investigator folder provided to each site.

8.4.2 Non-Serious AEs

All non-serious AEs that occur from consent through EOS must be assessed and recorded on the source documents and eCRF, regardless of causal relationship to the investigational product.

8.4.3 Special situations – Adverse Event Reporting

8.4.3.1 Medication Errors

All AEs (serious and non-serious) that occur in association with medication errors should be recorded in the AE page eCRF. Serious AEs should also be reported to Novartis safety as described in section 8.4.1. No record of Medication Error itself should be included on the AE eCRF page.

8.4.3.2 Pregnancy/Lactation Exposure

Occurrences of pregnancy/lactation exposure in a study subject from Day 1 through EOS must be reported to the Sponsor within 24 hours using the Pregnancy/Lactation Exposure Report Form.

In cases where a pregnancy/lactation exposure occurs with a SAE, the SAE Report Form should be used to report the SAE and the Pregnancy/Lactation Exposure Report Form should be used to report the pregnancy/lactation exposure.

When a pregnancy/lactation exposure occurs without any concurrent SAE, the Pregnancy/Lactation Exposure Report Form must be submitted alone.

The pregnancy should be followed up to determine outcome, including spontaneous or voluntary termination, details of the birth, and the presence or absence of any birth defects, congenital abnormalities, or maternal and/or newborn complications. Newborns should be followed for 12 months.

8.5 Expectedness

8.5.1 Expectedness Determination

Novartis safety department will be responsible for determining whether an AE is expected or unexpected for the purpose of suspected unexpected serious adverse reaction (SUSAR) reporting. An AE will be considered unexpected if the nature, severity, or frequency of the event is not consistent with the safety information previously described for the investigational product in the current/approved version of the Investigator's Brochure.

8.6 Study Stopping Criteria

8.6.1 Independent Data Monitoring Committee (IDMC) Stopping Rules

The IDMC will use all available evidence and their collective judgment in making a recommendation to stop or modify the ORION-8 study for safety. Any statistical considerations are not a substitute for the committee's medical, scientific, or statistical expertise. Details will be provided in the respective charter(s).

8.6.2 Sponsor Discontinuation Stopping Criteria

The Sponsor will review data on an ongoing basis and may, on discussion with the IDMC terminate the study for any clinically significant drug related safety signal (eg, serious hypersensitivity reactions or drug induced liver injury, etc).

Premature termination of a study may also occur because of a regulatory authority decision, change in opinion of the IRB/EC, drug safety problems, or at the discretion of the Sponsor. In addition, the Sponsor retains the right to discontinue development of inclisiran at any time.

If a study is prematurely terminated or discontinued, the Sponsor will promptly notify the investigator. After notification, the investigator must contact all participating subjects and the hospital pharmacy (if applicable) within 30 days of the notification. Final study visits should occur within 30 days of subject contact. As directed by the Sponsor, all study materials must be collected and all eCRFs completed to the greatest extent possible.

The Sponsor, or designee, will inform the health authorities and the IRBs/EC that the study has been stopped and the reasons for doing so, within the locally applicable timelines.

9 Data Collection

An electronic data capture (EDC) system which is 21 CFR Part 11 compliant will be used for this study. Certain data points from the previous protocol participation (ORION-3, ORION-9, ORION-10, or ORION-11) may be imported to the EDC system for this study. All users will be trained on the technical features of the EDC as well as the content of the eCRF by qualified personnel prior to gaining access to the EDC. A UserID/Password will be granted after training. This UserID is not to be shared amongst the study staff. All users must have a unique account to enter or review data. The eCRF should be filled out by the site 3 days after each visit. It is not expected that the eCRF will serve as source for any data collected in this study. If there is a reason for a site to do so, it must be approved by Sponsor and documented in the site files.

Prior to the database being locked, the investigator or designee will review, approve and sign/date each completed eCRF. This signature serves as attestation of the investigator's responsibility for ensuring that all data entered into the eCRF are complete, accurate and authentic. After the end of the study, a copy of the data will be provided to the site. This copy will contain the final data, an audit trail of activity on the data, and any queries and answers that were posted for data clarification. For this study, the end of the study will be defined as the last visit of the last subject.

10 Statistical Plan

This study will be a long-term extension study in up to 3300 subjects with ASCVD, ASCVD-risk equivalents (eg, diabetes and familial hypercholesterolemia), HeFH, [REDACTED] and elevated LDL-C despite maximum tolerated dose of LDL-C lowering therapies who have completed one of the Phase III lipid lowering studies [MDCO-PCS-17-03(ORION-9), MDCO-PCS-17-04 (ORION-10), MDCO-PCS-17-08 (ORION-11), or Phase II ORION-3 trial (MDCO-PCS-16-01)] and fulfill the entry criteria for this study in order to evaluate the efficacy, safety, and tolerability of long-term dosing of inclisiran. Following completion of study procedure for the final visit in the feeder study, informed consent will be obtained from subjects before the initiation of any study-specific procedures. The EOS visit in the previous study will be Day 1 in ORION-8. This will be a global, multicenter study in approximately 300 centers.

The duration that a subject is expected to participate in this study is a maximum of 3 years or the occurrence of one of the following events, whichever occurs first:

- a recommendation of discontinuation by the investigator or Sponsor,
- a decision by the subject to discontinue for any reason,
- an administrative decision is made to end the study

A separate Statistical Analysis Plan (SAP) document will provide more detailed specifications in data analysis and presentation.

10.1 Sample Size

Up to 3300 subjects with atherosclerotic cardiovascular disease who have completed one of the Phase III lipid-lowering feeder studies [MDCO-PCS-17-03 (ORION-9), MDCO-PCS-17-04 (ORION-10), MDCO-PCS-17-08 (ORION-11) or Phase II ORION-3 trial (MDCO-PCS-16-01)] and fulfill the entry criteria for this study will participate in this study.

10.2 General Statistical Considerations and Definitions

10.2.1 General Statistical Methods

All study-collected data will be summarized using descriptive statistics, graphs, and/or raw data listings. Descriptive statistics for continuous variables will include number of subjects (n), mean, standard deviation (SD), median, quartiles (Q1 and Q3), minimum (min) and maximum (max) values. Analysis of categorical variables will include frequency and percentage.

10.2.2 Analysis Population - Safety population

The safety population will be used for data analyses and/or presentation.

All subjects who received at least one dose of study drug will comprise the safety population. Treatment classification will be based on the actual treatment received. This will be the primary population for the efficacy and safety analyses.

10.2.3 Analysis Windows

The observational period for the study includes Day 1 (EOS visit in the previous study), the Treatment phase which consists of the first dose (Day 1), Day 90 dose, and subsequent dosing

visits every 180 days until Day 990 and EOS (Day 1080) visit. Any event occurring beyond the defined observational period, even if collected in the e-CRF, will not be included in the planned statistical analysis. However, all data, including that reported after the defined observational period, will be included in the subject data listings.

10.2.4 Missing Data Handling

Unless otherwise specified, missing data will not be imputed and will be excluded from the associated analysis.

10.3 Statistical Analyses

10.3.1 Demographic and Background Characteristics

Subject demographics and baseline characteristics except age collected from prior corresponding Phase III studies for each subject will be used for the summary using the safety population. For subjects moved over from the Phase II ORION-3 study, subject demographics and baseline characteristics collected at the ORION-3 study baseline will be used for this summary. Age will be recalculated by adding the duration that each subject spent in the prior corresponding Phase II or Phase III study

10.3.2 Study Drug and Concomitant Medications

Summary of each prior (prebaseline in the previous corresponding Phase II or Phase III study) medication and concomitant medication will be provided. Medication will be coded with World Health Organization (WHO) drug dictionary. Subjects will be counted only once within each period by medication.

10.3.3 Efficacy Analysis

10.3.3.1 Primary Efficacy Endpoints

The primary efficacy analysis of this study is to assess the proportion of subjects who attain global lipid targets for their level of ASCVD at EOS. Confidence interval will be provided.

10.3.3.2 Secondary Efficacy Endpoints

The actual value, absolute and percentage change in LDL-C and other lipids parameters from baseline (defined as baseline in the corresponding Phase II or Phase III feeder study) to EOS will be summarized over time. Descriptive statistics will be provided.

10.3.4 Safety Analysis

The safety objectives of this study are to evaluate the safety and tolerability profile of inclisiran. The safety analysis will be descriptive.

10.3.4.1 Adverse Events

The Medical Dictionary for Regulatory Activities (MedDRA) dictionary will be used for coding AEs. An AE (classified by preferred term) occurring during the study drug treatment period will

be counted as a treatment emergent AE (TEAE) either if it is not present at Day 1 of this study or if it is present at Day 1 of this study but increased in severity during the treatment period.

The number (percentage) of subjects reporting TEAEs for each preferred term will be tabulated by system-organ class, by system-organ class and severity, and by system-organ class and relationship to study drug. If more than one event occurred with the same preferred term for the same subject, the subject will be counted only once for that preferred term using the most severe or related occurrence for the summary by severity, or relationship to study drug, respectively.

10.3.4.2 Laboratory Tests

Laboratory values will be summarized at each time point. Analyses will also be performed for each lab parameter for incidence rates of potentially clinically significant (PCS) values for subjects without PCS value at baseline (defined as baseline in the corresponding Phase II or Phase III feeder study), as well as without PCS value at Day 1 of the study

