4.4.1 Individual Subject Dosing Stopping Criteria

During the study subjects will have clinic visits at regular intervals. Dosing with inclisiran should be temporarily discontinued or stopped in subjects with:

1. Intolerable AEs, or if the investigator believes that continuing dosing will be detrimental to the subject's mental or physical health. This includes severe or serious reactions at the injection site and any anaphylactic type reactions.
2. Unexplained increases in transaminases (ALT or AST) or total bilirubin as follows:
 - a. ALT or AST >8xULN

- b. ALT or AST >5xULN for more than 2 weeks
- c. ALT or AST >3xULN and (total bilirubin >2xULN or INR >1.5)
- d. ALT or AST >3xULN with the appearance of fatigue, nausea, vomiting, right upper quadrant pain or tenderness, fever, rash, and/or eosinophilia (>5%)

The investigator should evaluate to see if other causes for the laboratory abnormalities are immediately apparent, such as obstructive gall bladder or bile duct disease, viral or alcoholic hepatitis, malignancy involving the liver, congestive hepatopathy, other hepatotoxins or heritable disorders.

- 3. Unexplained creatine kinase (CK) values >5 x ULN confirmed by repeat test when the CK elevation is associated with muscle pain, muscle tenderness and/or muscle weakness, or new onset renal dysfunction.

In the case that study medication is permanently discontinued the subject will be asked to return to complete an EOS visit, which should occur at least 90 days following the last dose of inclisiran.

All subjects should be followed until all clinically significant laboratory abnormalities return to normal or to the baseline state. Subjects discontinuing the trial due to withdrawal of consent or initiation of other PSCK9 lipid lowering therapies will not be followed up within the trial.

5 Treatment of Subjects

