7.1.6.1 Hematology

Blood draws for hematology will include:

- Hemoglobin, hematocrit, erythrocytes, reticulocytes, mean cell hemoglobin (MCH), mean corpuscular volume (MCV), mean corpuscular hemoglobin concentration (MCHC), platelet count, white blood cell count with differential.

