7.1.6.2 Coagulation

Blood draws for coagulation will include:

- Prothrombin time (PT), international normalized ratio (INR), activated partial thromboplastin (aPTT)

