7.1.6.3 Chemistry

Blood draws for chemistry will be performed per the Schedule of Assessments (Table 6-1). Analysis will vary based visit day as follows:

- **Full serum chemistry**
AST, ALT, alkaline phosphatase (ALP), gamma glutamyl transferase (GGT), total bilirubin (TBIL), direct and indirect bilirubin, creatine phosphokinase (CPK), lactate, bicarbonate, uric acid, creatinine, urea (BUN), estimated glomerular filtration rate (eGFR), sodium, potassium, calcium, inorganic phosphate, chloride, albumin, total protein, glucose (fasting), glycated hemoglobin A1C (HbA1C), high sensitivity C-reactive protein (hsCRP) and tryptase (as required)
- **Limited serum chemistry**
ONLY: AST, ALT, ALP, GGT, TBIL, CPK, creatinine, eGFR, HbA1C and tryptase (as required)

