### 2.7.3.1 Summary tables using descriptive statistics

Summaries for safety laboratory values will include observed value, changes and percent changes from ORION-8 baseline over time:

- Hematology and coagulation parameters will be summarized at ORION-8 baseline (for observed value only), at Day 1080, and at EOS.
- Safety chemistry parameters in the full serum chemistry panel but not in limited serum chemistry panel will be summarized at ORION-8 baseline (for observed value only), at Day 1080, and at EOS.
  - These include direct and indirect bilirubin, lactate, bicarbonate, uric acid, urea (blood urea nitrogen; BUN), sodium, potassium, calcium, inorganic phosphorus, chloride, albumin, total protein, fasting glucose.
- Safety chemistry parameters in limited chemistry panel, which is a subset of the full chemistry panel, will be summarized at ORION-8 baseline (for observed value only), at each scheduled visit from Day 90 to Day 1080, and at EOS.
  - These include aspartate aminotransferase (AST), alanine aminotransferase (ALT), alkaline phosphatase (ALP), gamma glutamyl transferase (GGT), total bilirubin (TBIL), creatine kinase (CK), creatinine, eGFR, glycated hemoglobin A1C (HbA1c).

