## **4 Change to protocol specified analyses**

No change from protocol specified analysis was made.

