### 5.3 Criteria for potentially clinically significant and clinically significant abnormal laboratory tests

Hemoglobin A1c criteria is explicitly stated in the table below. For all other parameters, a PCS/CS criterion is met when both of the following occur (baseline refers to ORION-8 baseline):

- There is a post-baseline value that meets the threshold
- The baseline value does not meet the threshold

Some examples are:

- For leukocytes, a subject satisfies “ $\leq 2.8 \times 10^9/L$ ” criterion as long as the baseline value is  $> 2.8 \times 10^9/L$  and any post-baseline value is  $\leq 2.8 \times 10^9/L$ ; a subject satisfies “ $\geq 16 \times 10^9/L$ ” criterion as long as the baseline value is  $< 16 \times 10^9/L$  and any post-baseline value is  $\geq 16 \times 10^9/L$ .
- For CK, a subject satisfies “ $> 3$  and  $\leq 5 \times ULN$ ” criterion as long as the baseline value is  $\leq 3 \times ULN$  and any post-baseline value is  $> 3$  and  $\leq 5 \times ULN$ . A subject satisfies “ $> 5$  and  $\leq 10 \times ULN$ ” criterion as long as the baseline value is  $\leq 5 \times ULN$  and any post-baseline value is  $> 5$  and  $\leq 10 \times ULN$ . If a subject satisfies both “ $> 3$  and  $\leq 5 \times ULN$ ” and “ $> 5$  and  $\leq 10 \times ULN$ ” criteria and does not satisfy the criteria of any more severe category, the subject will be presented under “ $> 5$  and  $\leq 10 \times ULN$ ” but not under “ $> 3$  and  $\leq 5 \times ULN$ ” because the most severe category will be used for CK.
- For serum creatinine, the CS criterion is satisfied if at least one of the following is true:

- The baseline value is  $\leq 2$  mg/dL and any post-baseline value is  $> 2$  mg/dL.
- Any post-baseline value is  $\geq 50\%$  increase from baseline, regardless of whether the baseline value is  $\leq 2$  mg/dL.

Parameter	Unit	Lower Boundary	Upper Boundary
Hematology			
Hematocrit	%	$\leq 0.8 \times \text{LLN}$	N/A
Hemoglobin	g/dL	$\leq 10$ g/dL	N/A
Platelet Count	$10^9/\text{L}$	$\leq 75^*$	$\geq 700^*$
White Blood Cell (Leukocyte) Count	$10^9/\text{L}$	$\leq 2.8$	$\geq 16$
Serum Chemistry			
Alanine Aminotransferase (ALT/SGPT)	U/L	N/A	$> 1$ and $\leq 3 \times \text{ULN}$
Alanine Aminotransferase (ALT/SGPT)	U/L	N/A	$> 3$ and $\leq 5 \times \text{ULN}^*$
Alanine Aminotransferase (ALT/SGPT)	U/L	N/A	$> 5$ and $\leq 10 \times \text{ULN}^*$
Alanine Aminotransferase (ALT/SGPT)	U/L	N/A	$> 10$ and $\leq 20 \times \text{ULN}^*$

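### The protocol specifies PCS incidence for each laboratory parameter; the SAP sets limits for 11 of 36 (none for coagulation), uses one of the two baselines, and declares no change

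*Protocol*

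**What the plan says.** Protocol 10.3.4.2 (Laboratory Tests) commits to the following: "Analyses will also be performed for each lab parameter for incidence rates of potentially clinically significant (PCS) values". It applies this to subjects without a PCS value at feeder-study baseline, as well as without one at Day 1 of ORION-8. It sets no limits itself, and Protocol Section 10 leaves detailed specification to the SAP.

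The tests are named in Protocol 7.1.6.1 to 7.1.6.3. The coagulation panel, for example, is "Prothrombin time (PT), international normalized ratio (INR), activated partial thromboplastin (aPTT".

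SAP 2.7.3.3 counts and lists subjects with PCS or clinically significant (CS) values by the criteria in Appendix 5.3. The appendix table has rows for haematocrit, haemoglobin, platelets, leukocytes, ALT, AST, ALP, CK, HbA1c, creatinine and total bilirubin. Its text takes baseline to mean ORION-8 baseline. For coagulation the SAP offers only SAP 2.7.3.1: "Hematology and coagulation parameters will be summarized at ORION-8 baseline (for observed value only), at Day 1080, and at EOS".

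Protocol 4.4.1 includes this combined liver criterion: "ALT or AST >3xULN and (total bilirubin >2xULN or INR >1.5", where the bracket closes after the INR value. The Hy's Law table in SAP 2.7.3.4 combines ALT or AST with total bilirubin and ALP. INR does not appear in it.

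SAP Section 4 states: "No change from protocol specified analysis was made".

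**The concern.** The protocol's commitment names no subset of tests. Leaving detail to the SAP lets the SAP choose the limits. It does not obviously let the SAP leave out most of the parameters and one of the two baselines while declaring that nothing changed.

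Safety is one of the two primary objectives, and the synopsis names coagulation testing and chemistry within the safety endpoint. The study is noncomparative and the safety analysis descriptive, so counting subjects who become abnormal is a main way to show a signal in individuals. Without a limit or a range count, the report cannot say how many subjects became abnormal on PT, INR, aPTT, potassium, sodium, GGT or albumin.

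The baseline also matters. Subjects in the Phase III Inclisiran-Inclisiran group and the ORION-3 rollovers were already on inclisiran before ORION-8. A value that crossed a limit in the feeder study and stayed there is part of their ORION-8 baseline, so Appendix 5.3 does not count it. A count against feeder baseline would.

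**Working it through.** The documents state no figure on this point, so the check is a direct count.

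**1. Named parameters.**
- Haematology (Protocol 7.1.6.1): "Hemoglobin, hematocrit, erythrocytes, reticulocytes, mean cell hemoglobin (MCH), mean corpuscular volume (MCV), mean corpuscular hemoglobin concentration (MCHC), platelet count" and white cell count, with the differential counted as one: 9.
- Coagulation (7.1.6.2): 3.
- Full serum chemistry (7.1.6.3), without tryptase, which is taken only as required: 24.
- Total: 9 + 3 + 24 = 36.

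**2. Parameters with a limit in Appendix 5.3.** Haematology 4, coagulation 0, chemistry 7, total 11. Without a limit: 36 - 11 = 25, and 25/36 = 69%.

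**3. Other category counts.** eGFR has a shift table to EOS (SAP 2.7.3.2). Fasting glucose enters the glucose-control shifts and the new-onset diabetes count (SAP 2.7.4.3 and 2.7.4.4). Removing both gives 25 - 2 = 23, and 23/36 = 64%. The 23 are:
- haematology (5): erythrocytes, reticulocytes, MCH, MCV, MCHC;
- coagulation (3): PT, INR, aPTT;
- chemistry (15): GGT, direct and indirect bilirubin, lactate, bicarbonate, uric acid, urea, sodium, potassium, calcium, phosphate, chloride, albumin, total protein, hsCRP.

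**4. Does the counting convention matter?**

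| Convention | Named | No PCS/CS limit | No limit and no category count |
|---|---|---|---|
| As above | 36 | 25 (69%) | 23 (64%) |
| Adding tryptase | 37 | 26 (70%) | 24 (65%) |
| SAP safety list (hsCRP treated as efficacy) | 35 | 24 (69%) | 22 (63%) |
| As above plus 10 urinalysis items | 46 | 35 (76%) | 33 (72%) |
| Adding tryptase and urinalysis | 47 | 36 (77%) | 34 (72%) |

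Most tests are uncovered under every convention.

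**5. Baselines.** The protocol sentence can mean two analyses, one per baseline, or one analysis of subjects free of a PCS value at both. Using ORION-8 baseline alone satisfies neither reading.

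**6. Combined criterion.** Protocol 4.4.1 pairs ALT or AST >3xULN with either bilirubin >2xULN or INR >1.5. SAP 2.7.3.4 tabulates the bilirubin arm (with ALP <2xULN added). No SAP table tabulates the INR arm. Table 6-1 schedules coagulation after Day 1 only at EOS, so there is normally one post-baseline INR per subject.

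**7. What descriptive statistics would show.** As an illustration, suppose 1% of 3000 subjects (30) went from INR 1.0 to 2.0. The mean would rise by 0.01 x 1.0 = 0.01, and the quartiles would hardly move. The maximum would reach at least 2.0. If the baseline SD were 0.1 (assumed), the new SD would be sqrt(0.1² + 0.01 x 0.99 x 1.0²) = sqrt(0.0199), about 0.14. A reader would see that something had happened, but not that 30 subjects were affected or where they started. The 1% rate is an assumption, not a forecast.

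**The case against.** The strongest reply is that PCS incidence can be computed only where a PCS criterion exists. The protocol sets none and leaves detail to the SAP, so Appendix 5.3 defines the set and the no-change statement is defensible. This has some force for the choice of limits. It does not fit the words of the protocol sentence, which cover each parameter, and it does not explain the missing feeder baseline. Even on this reading, the restriction should be stated.

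A reader might infer that abnormal values in most tests are never counted. The documents do not support that. eGFR and fasting glucose have category counts. Minimum and maximum are reported. An abnormal laboratory finding that is reported as an adverse event enters the TEAE tables, and Protocol 10.2.3 places all data in subject listings. The adverse-event route is only a partial substitute. The protocol requires an adverse event for abnormal urinalysis (7.1.6.4) and sets HbA1c triggers (8.3.2), but gives no such rule for coagulation or electrolytes.

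A reader might also take INR above 1.5 as a stand-alone protocol limit. It is not: it applies only with ALT or AST >3xULN. A stand-alone row could also pick up subjects who start an anticoagulant, which the protocol does not prohibit.

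Finally, out-of-range is not the same as PCS. Several Appendix 5.3 limits lie well beyond the normal range, such as 0.8xLLN for haematocrit and >2xULN for ALP. If reference ranges are 95% ranges (assumed), about 0.025 x 3000 = 75 healthy values would fall outside on each side of each test. That objection stands, and range counts must be labelled for what they are.

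**Conclusion.** The concern holds as a conflict between the two documents. The protocol's PCS commitment covers every laboratory parameter and two baselines. The SAP delivers 11 of 36 parameters, no coagulation test and one baseline, and declares no departure. After credit for eGFR and fasting glucose, 23 of 36 (64%; 63% to 72% across counting conventions) are not counted against any prespecified laboratory limit. The INR arm of the combined liver criterion is not counted either.

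The conclusion does not extend to saying that these values go unreported, or that the protocol sets an INR limit of its own. The 36 rests on the stated convention. The INR illustration rests on assumed figures and shows only why summary statistics cannot replace a count of subjects.

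**What to change.** 1. For parameters without a PCS limit, add a table counting subjects within the central laboratory range at baseline who have a post-baseline value below LLN or above ULN. Label it as out-of-range shifts, not as PCS.
2. In the liver laboratory table, add a count of ALT or AST >3xULN with INR >1.5 at the same time point. This is a reporting count only; do not present INR >1.5 as a stand-alone protocol limit.
3. Present the PCS counts against feeder-study baseline as well as ORION-8 baseline, and state which reading of the protocol sentence is followed.
4. Correct SAP Section 4 to declare and justify any parameter or baseline left out on purpose.

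The cost is SAP wording and one or two extra tables, with no new sampling. Item 3 assumes that feeder-baseline safety laboratory values are available for analysis. The SAP defines that baseline for laboratory parameters but does not use it for the PCS tables. The downside is some rows of minor out-of-range values. For coagulation the yield is limited, because there is normally a single post-baseline value at EOS.
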